5.3.4 Assessment of Causality of Adverse Events

Investigators should use their knowledge of the patient, the circumstances surrounding the event, and an evaluation of any potential alternative causes to determine whether an adverse event is considered to be related to the study drug, indicating "yes" or "no" accordingly. The following guidance should be taken into consideration (see also [Table 3](#)):

- Temporal relationship of event onset to the initiation of study drug
- Course of the event, with special consideration of the effects of dose reduction, discontinuation of study drug, or reintroduction of study drug (as applicable)
- Known association of the event with the study drug or with similar treatments
- Known association of the event with the disease under study
- Presence of risk factors in the patient or use of concomitant medications known to increase the occurrence of the event
- Presence of non-treatment-related factors that are known to be associated with the occurrence of the event

Table 3 Causal Attribution Guidance

Is the adverse event suspected to be caused by the study drug on the basis of facts, evidence, science-based rationales, and clinical judgment?	
YES	There is a plausible temporal relationship between the onset of the adverse event and administration of the study drug, and the adverse event cannot be readily explained by the patient's clinical state, intercurrent illness, or concomitant therapies; and/or the adverse event follows a known pattern of response to the study drug; and/or the adverse event abates or resolves upon discontinuation of the study drug or dose reduction and, if applicable, reappears upon re-challenge.
NO	An adverse event will be considered related, unless it fulfills the criteria specified below. Evidence exists that the adverse event has an etiology other than the study drug (e.g., preexisting medical condition, underlying disease, intercurrent illness, or concomitant medication); and/or the adverse event has no plausible temporal relationship to administration of the study drug (e.g., cancer diagnosed 2 days after first dose of study drug).

For patients receiving combination therapy, causality will be assessed individually for each protocol-mandated therapy.

5.3.5 Procedures for Recording Adverse Events

Investigators should use correct medical terminology/concepts when recording adverse events on the Adverse Event eCRF. Avoid colloquialisms and abbreviations.

Only one adverse event term should be recorded in the event field on the Adverse Event eCRF.

5.3.5.1 Diagnosis versus Signs and Symptoms

A diagnosis (if known) should be recorded on the Adverse Event eCRF rather than individual signs and symptoms (e.g., record only liver failure or hepatitis rather than jaundice, asterixis, and elevated transaminases). However, if a constellation of signs and/or symptoms cannot be medically characterized as a single diagnosis or syndrome at the time of reporting, each individual event should be recorded on the Adverse Event eCRF. If a diagnosis is subsequently established, all previously reported adverse events based on signs and symptoms should be nullified and replaced by one adverse event report based on the single diagnosis, with a starting date that corresponds to the starting date of the first symptom of the eventual diagnosis.

5.3.5.2 Adverse Events That Are Secondary to Other Events

In general, adverse events that are secondary to other events (e.g., cascade events or clinical sequelae) should be identified by their primary cause, with the exception of severe or serious secondary events. A medically significant secondary adverse event that is separated in time from the initiating event should be recorded as an independent event on the Adverse Event eCRF. For example:

- If vomiting results in mild dehydration with no additional treatment in a healthy adult, only vomiting should be reported on the eCRF.
- If vomiting results in severe dehydration, both events should be reported separately on the eCRF.
- If a severe gastrointestinal hemorrhage leads to renal failure, both events should be reported separately on the eCRF.
- If dizziness leads to a fall and consequent fracture, all three events should be reported separately on the eCRF.
- If neutropenia is accompanied by an infection, both events should be reported separately on the eCRF.

All adverse events should be recorded separately on the Adverse Event eCRF if it is unclear as to whether the events are associated.

5.3.5.3 Persistent or Recurrent Adverse Events

A persistent adverse event is one that extends continuously, without resolution, between patient evaluation timepoints. Such events should only be recorded once on the Adverse Event eCRF. The initial severity (intensity or grade) of the event will be recorded at the time the event is first reported. If a persistent adverse event becomes more severe, the most extreme severity should also be recorded on the Adverse Event eCRF. If the event becomes serious, it should be reported to the Sponsor immediately (i.e., no more than 24 hours after learning that the event became serious; see Section 5.3.2 for reporting instructions). The Adverse Event eCRF should be updated by changing the event from "non-serious" to "serious," providing the date that the event became serious, and completing all data fields related to serious adverse events.

A recurrent adverse event is one that resolves between patient evaluation timepoints and subsequently recurs. Each recurrence of an adverse event should be recorded as a separate event on the Adverse Event eCRF.

5.3.5.4 Abnormal Laboratory Values

Not every laboratory abnormality qualifies as an adverse event. A laboratory test result must be reported as an adverse event if it meets any of the following criteria:

- Is accompanied by clinical symptoms
- Results in a change in study treatment (e.g., dosage modification, treatment interruption, or treatment discontinuation)

- Results in a medical intervention (e.g., potassium supplementation for hypokalemia) or a change in concomitant therapy
- Is clinically significant in the investigator's judgment

It is the investigator's responsibility to review all laboratory findings. Medical and scientific judgment should be exercised in deciding whether an isolated laboratory abnormality should be classified as an adverse event.

If a clinically significant laboratory abnormality is a sign of a disease or syndrome (e.g., alkaline phosphatase and bilirubin 5× upper limit of normal [ULN] associated with cholestasis), only the diagnosis (i.e., cholestasis) should be recorded on the Adverse Event eCRF.

If a clinically significant laboratory abnormality is not a sign of a disease or syndrome, the abnormality itself should be recorded on the Adverse Event eCRF, along with a descriptor indicating whether the test result is above or below the normal range (e.g., "elevated potassium," as opposed to "abnormal potassium"). If the laboratory abnormality can be characterized by a precise clinical term per standard definitions, the clinical term should be recorded as the adverse event. For example, an elevated serum potassium level of 7.0 mEq/L should be recorded as "hyperkalemia."

Observations of the same clinically significant laboratory abnormality from visit to visit should only be recorded once on the Adverse Event eCRF (see Section [5.3.5.4](#) or details on recording persistent adverse events).

5.3.5.5 Abnormal Vital Sign Values

Not every vital sign abnormality qualifies as an adverse event. A vital sign result must be reported as an adverse event if it meets any of the following criteria:

- Is accompanied by clinical symptoms
- Results in a change in study treatment (e.g., dosage modification, treatment interruption, or treatment discontinuation)
- Results in a medical intervention or a change in concomitant therapy
- Is clinically significant in the investigator's judgment

It is the investigator's responsibility to review all vital sign findings. Medical and scientific judgment should be exercised in deciding whether an isolated vital sign abnormality should be classified as an adverse event.

If a clinically significant vital sign abnormality is a sign of a disease or syndrome (e.g., high blood pressure), only the diagnosis (i.e., hypertension) should be recorded on the Adverse Event eCRF.

Observations of the same clinically significant vital sign abnormality from visit to visit should only be recorded once on the Adverse Event eCRF (see Section 5.3.5.5 for details on recording persistent adverse events).

5.3.5.6 Abnormal Liver Function Tests

The finding of an elevated ALT or AST ($>3 \times \text{ULN}$) in combination with either an elevated total bilirubin ($>2 \times \text{ULN}$) or clinical jaundice in the absence of cholestasis or other causes of hyperbilirubinemia is considered to be an indicator of severe liver injury (as defined by Hy's Law). Therefore, investigators must report as an adverse event the occurrence of either of the following:

- Treatment-emergent ALT or AST $>3 \times \text{ULN}$ in combination with total bilirubin $>2 \times \text{ULN}$
- Treatment-emergent ALT or AST $>3 \times \text{ULN}$ in combination with clinical jaundice

The most appropriate diagnosis or (if a diagnosis cannot be established) the abnormal laboratory values should be recorded on the Adverse Event eCRF (see Section 5.3.5.4) and reported to the Sponsor immediately (i.e., no more than 24 hours after learning of the event), either as a serious adverse event or an adverse event of special interest (see Section 5.3.2).

5.3.5.7 Deaths

All deaths that occur during the protocol-specified adverse event reporting period (see Section 5.2.1), regardless of relationship to study drug, must be recorded on the Adverse Event eCRF and immediately reported to the Sponsor (see Section 5.3.2). This includes death attributed to progression of COPD.

Death should be considered an outcome and not a distinct event. The event or condition that caused or contributed to the fatal outcome should be recorded as the single medical concept on the Adverse Event eCRF. Generally, only one such event should be reported. If the cause of death is unknown and cannot be ascertained at the time of reporting, "**unexplained death**" should be recorded on the Adverse Event eCRF. If the cause of death later becomes available (e.g., after autopsy), "unexplained death" should be replaced by the established cause of death. The term "**sudden death**" should not be used unless combined with the presumed cause of death (e.g., "sudden cardiac death").

If the death is attributed solely to progression of COPD, "Chronic Obstructive Pulmonary Disease progression" should be recorded on the Adverse Event eCRF.

Deaths that occur after the adverse event reporting period should be reported as described in Section 5.5.

5.3.5.8 Preexisting Medical Conditions

A preexisting medical condition is one that is present at the screening visit for this study. Such conditions should be recorded on the General Medical History and Baseline Conditions eCRF.

A preexisting medical condition should be recorded as an adverse event only if the frequency, severity, or character of the condition worsens during the study. When recording such events on the Adverse Event eCRF, it is important to convey the concept that the preexisting condition has changed by including applicable descriptors (e.g., "more frequent headaches").

5.3.5.9 Lack of Efficacy or Worsening of COPD

Medical occurrences or symptoms of deterioration that are anticipated as part of COPD should be recorded as an adverse event if judged by the investigator to have unexpectedly worsened in severity or frequency or changed in nature at any time during the study. When recording an unanticipated worsening of COPD on the Adverse Event eCRF, it is important to convey the concept that the condition has changed by including applicable descriptors (e.g., "accelerated worsening of Chronic Obstructive Pulmonary Disease").

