2.2 SAFETY OBJECTIVE

The safety objective for this study is to evaluate the safety of ^{129}Xe MRI procedures and of AZM+SOC compared with SOC on the basis of the following endpoints:

- Incidence and severity of adverse events, with severity determined according to the World Health Organization (WHO) toxicity scale
- Change from baseline in targeted vital signs
- Change from baseline in targeted clinical laboratory test results
- Change from baseline in ECG data

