4.5.13 Acute Exacerbations of COPD

All patients will be provided with a diary to track daily study treatment and the date(s) of any AEx events. Patients will be required to bring their diaries to study visits. Patients will be asked if they have experienced an AEx during the last month at each study visit.

The investigator will ask directed questions to assess whether the patient experienced any adverse events and any protocol-defined COPD exacerbations since the last study visit.

Given that COPD exacerbations are the key primary endpoint in this study, a dedicated eCRF will be used to record information regarding protocol-defined exacerbation events. A COPD exacerbation must also be reported as an adverse event (or serious adverse event as applicable) as per Section [5.2](#). Sites should update the COPD Targeted Concomitant Medications eCRF with all medications used for treatment.

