5.2.1 Adverse Events

According to the ICH guideline for GCP, an adverse event is any untoward medical occurrence in a clinical investigation patient administered a pharmaceutical product, regardless of causal attribution. An adverse event can, therefore, be any of the following:

- Any unfavorable and unintended sign (including an abnormal laboratory finding), symptom, or disease temporally associated with the use of a medicinal product, whether or not considered related to the medicinal product
- Any new disease or exacerbation of an existing disease (a worsening in the character, frequency, or severity of a known condition) (see Section [5.3.5.9](#) for more information)
- Recurrence of an intermittent medical condition (e.g., headache) not present at baseline
- Any deterioration in a laboratory value or other clinical test (e.g., ECG, X-ray) that is associated with symptoms or leads to a change in study treatment or concomitant treatment or discontinuation from study drug

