6.5 SAFETY ANALYSES

The safety analysis population will consist of all patients who received at least one dose of study drug during the 48-week open-label treatment period, with patients grouped according to treatment received (AZM + SOC or SOC).

Safety will be assessed through summaries of exposure to study treatment, adverse events, changes in laboratory test results, and changes in vital signs and ECGs (see Section [2.2](#)).

Study treatment exposure (such as treatment duration, total dose received, and number of cycles and dose modifications) will be summarized with descriptive statistics.

All verbatim adverse event terms will be mapped to Medical Dictionary for Regulatory Activities (MedDRA) thesaurus terms, and adverse event severity will be graded according to the WHO toxicity grading scale. All adverse events, serious adverse events, adverse events leading to death, adverse events of special interest, and adverse events leading to study treatment discontinuation that occur on or after the first dose of study treatment (i.e., treatment emergent adverse events) will be summarized by mapped term, appropriate thesaurus level, and severity grade. For events of varying severity, the highest grade will be used in the summaries. Deaths and cause of death will be summarized.

Relevant laboratory, vital sign (pulse rate, respiratory rate, blood pressure, pulse oximetry, and temperature), and ECG data will be displayed by time, with grades identified where appropriate. Additionally, a shift table of selected laboratory tests will be used to summarize the baseline and maximum postbaseline severity grade. Changes in vital signs and ECGs will be summarized.

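### The recording rules leave unclear whether every protocol-defined COPD exacerbation is an adverse event, which affects the overall adverse event totals by arm

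*Combined protocol and SAP*

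**What the plan says.** Section 4.5.13 is unconditional: "A COPD exacerbation must also be reported as an adverse event (or serious adverse event as applicable) as per Section" 5.2. It also sets up a dedicated eCRF for protocol-defined exacerbations.

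Section 5.2.1 lists as an adverse event "Any new disease or exacerbation of an existing disease (a worsening in the character, frequency, or severity of a known condition") and points to Section 5.3.5.9 for more information.

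Section 5.3.5.9 covers deterioration that is anticipated as part of COPD. Such deterioration "should be recorded as an adverse event if judged by the investigator to have unexpectedly worsened in severity or frequency or changed in nature".

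Section 4.6.1 requires treatment to stop for a related Grade 4 adverse event and takes COPD exacerbations out of that rule, which presupposes that they are adverse events.

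The safety objective in Section 2.2 evaluates "AZM+SOC compared with SOC on the basis of the following endpoints", the first of which is the incidence and severity of adverse events. Under Section 6.5, "All adverse events, serious adverse events, adverse events leading to death, adverse events of special interest" and events leading to discontinuation "will be summarized by mapped term, appropriate thesaurus level, and severity grade". Section 6.5 does not mention exacerbations.

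**The concern.** The mandatory rule in 4.5.13 leads, through its own cross-references, to a rule that rests on investigator judgment. Cohort A patients must have had at least 2 moderate or severe exacerbations in a 12-month period, so an exacerbation at a patient's usual frequency can reasonably be read as anticipated. A site that works from Section 5, where adverse event recording is set out, could then leave some exacerbations unrecorded as adverse events. The neighbouring Section 5.3.5.8 encourages a narrow reading, since a preexisting condition "should be recorded as an adverse event only if the frequency, severity, or character of the condition worsens during the study".

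Two things are at stake. First, exacerbations are also the efficacy outcome, and the plan assumes azithromycin reduces them by 35%. The more of them that are recorded, the more the overall totals lean towards AZM + SOC, and the more an excess of other events on azithromycin is offset. Second, the trial is open-label, so whether a deterioration is judged unexpected could depend on the arm.

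Serious adverse events are touched as well. Under 5.2.2 and 5.3.5.10 a hospitalised exacerbation is serious only if it is an adverse event to begin with. Deaths in the reporting period are protected separately by 5.3.5.7.

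**Working it through.** **The passages in sequence.** 4.5.13 (must be reported, as per 5.2) → 5.2.1 (exacerbation of an existing disease is an adverse event; see 5.3.5.9) → 5.3.5.9 (anticipated COPD deterioration is recorded on a judgment that it worsened unexpectedly or changed in nature). No step exempts protocol-defined exacerbations, and no text ranks the rules.

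**Size.** The documents state no adverse event count or rate, so there is no planned figure to reproduce. The plan's exacerbation assumptions (Section 6.1) give an upper bound.

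Inputs:
- Cohort A of about 100, randomised 1:1, 10% drop-out: 100/2 × 0.9 = 45 per arm.
- Mean exacerbation frequency 2 over 48 weeks of observation. The time unit is not stated; taken as per year, the SOC mean is 2 × 48/52 = 1.85.
- 35% reduction, rate ratio 0.65: the AZM + SOC mean is 1.85 × 0.65 = 1.20.
- Over-dispersion 1.3. The parameterisation is not stated, so both k = 1.3 and k = 1/1.3 = 0.77 are used.

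Exacerbations if all are recorded:
- SOC: 45 × 2 × 48/52 = 83.
- AZM + SOC: 83 × 0.65 = 54, which is 29 fewer.
- If the mean of 2 is per 48 weeks: 90 and 58.5 with 45 per arm, or 100 and 65 with 50 per arm.

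Patients with at least one exacerbation, P = 1 − (1 + kμ)^(−1/k), with μ = 1.85 and 1.20:

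| k | SOC | AZM + SOC | Gap |
|---|---|---|---|
| 1.3 | 61.0% | 51.5% | 9.5 points |
| 0.77 | 68.3% | 57.3% | 11.0 points |

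**From exacerbations to any adverse event.** Suppose a share q of patients in each arm has some other adverse event, independently of exacerbations. The gap in patients with any adverse event is then (1 − q) × (9.5 to 11.0) points: about 5 at q = 0.5, about 2 at q = 0.8 and about 1 at q = 0.9. The documents give no q, so these values are assumptions.

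**Effect on the crude event total.** Let b be other adverse events per patient over 48 weeks (assumed 0.5 to 6), e the extra non-exacerbation events per patient on azithromycin, and f the share of exacerbations recorded. The all-event rate ratio is (b + e + 1.20f)/(b + 1.85f).
- e = 0: from 0.72 (b = 0.5) to 0.92 (b = 6) if all are recorded; 1.00 if none are.
- e = 0.5 (assumed): 0.94 to 0.98 if all are recorded; 1.08 to 2.00 if none are.

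An azithromycin excess is therefore outweighed in the crude total only when e is below f × (1.85 − 1.20) = 0.65f events per patient. At e = 1.0 the ratio stays above 1 even with every exacerbation recorded (1.05 to 1.15).

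**Judgment differing by arm.** If 50% of exacerbations were recorded on SOC and 77% on AZM + SOC, the counts would be 0.50 × 83.1 = 41.5 and 0.77 × 54.0 = 41.6, and the assumed 35% reduction would vanish from the adverse event data. These shares are illustrative. If both arms record the same share, the ratio among recorded exacerbations stays at 0.65.

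**The case against.** The strongest reply is that there is no real conflict. Section 4.5.13 is specific and mandatory for protocol-defined exacerbations, 5.2.1 lists exacerbation of an existing disease as an adverse event, and the carve-out in 4.6.1 makes sense only if exacerbations are adverse events. Section 5.3.5.9 can then be read as a general rule for background symptoms. This is the better reading, and the fix adopts it. What survives is that the text does not say so, and the cross-reference from 5.2.1 carries no exemption.

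A reader might infer that 5.3.5.9 allows only unexpectedly worsened events to be recorded, so that ordinary exacerbations are excluded. The documents do not support that. The section does not say only, does not name exacerbations, and also admits a change in nature. An event needing systemic treatment or hospitalisation could well be judged to meet it. Recording would probably fall somewhere below the total, not to zero.

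A reader might also infer that 6.5 would hide azithromycin's harms behind exacerbations. Summaries by mapped term would normally give exacerbations their own line. Hearing, QT, liver and C. difficile events have their own terms and targeted rules, and a Safety Monitoring Committee reviews cumulative data about every 6 months. Only the crude totals mix the two.

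Finally, safety here is descriptive, in an exploratory trial focused on estimation, and the dedicated eCRF would allow exacerbations to be separated later. That stands for events entered as adverse events. For exacerbations never entered as such, grade and causality may not be fully recoverable.

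**Conclusion.** The passages need reconciling, but the point is minor. The weight of the text favours recording every protocol-defined exacerbation as an adverse event; the plan does not state this where sites look for recording rules, and an open-label judgment is left in between.

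The 83 (SOC) and 54 (AZM + SOC) are ceilings on what could enter the overall totals. They rest on the plan's own rate, effect and drop-out assumptions, with the mean of 2 taken as annual and drop-outs contributing nothing. For serious adverse events no size can be given, because the documents state no rate of severe exacerbations.

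Two larger conclusions are tempting and not supported. The gap of about 10 to 11 points is in patients with an exacerbation; it equals the gap in patients with any adverse event only if nobody has another adverse event. Nor can one say that exacerbations dominate the comparison: they would be more than half of all SOC adverse events only if other events ran below about 1.85 per SOC patient over 48 weeks, and the documents give no such rate. The efficacy endpoint has its own eCRF and is not affected.

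**What to change.** 1. In Section 5.3.5.9, state that the section does not apply to protocol-defined moderate or severe COPD exacerbations, all of which are recorded as adverse events (serious where applicable) per 4.5.13. The cross-reference in 5.2.1 then leads to a consistent rule.
2. In Section 6.5, add overall adverse event and serious adverse event totals by arm, with and without protocol-defined exacerbations, identified from the dedicated eCRF.

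The cost is one sentence and a few extra summary tables from data already collected. The wording change matters most while recording is still under way; the tables can be added at any time before analysis.
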